## 6.0 CLINICAL AND LABORATORY EVALUATIONS

## 6.1 Schedule and Timing of Follow-up Visits and Testing

The patient will have a signed informed consent form in place prior to any study specific testing. Day 0 is defined as the day of percutaneous reperfusion. All patients enrolled in this trial will undergo serial follow-up examination and testing to determine the long-term safety of this therapy as mandated by the FDA. Patients will take twice-daily measurements of temperature for one month following infusion of product. The patients will be required to see their primary physician or one of the Investigators within 48 hours if the patient develops a persistent fever greater than 100.0° F.

## 6.2 Consent Visit (Day 0 to Day 2)

- Consent signed
- Inclusion / Exclusion Review
- Complete Medical History and Medication Review
- Physical Exam, including vital signs, height, weight and pulse oximetry
- Laboratory Tests (include complete blood count (CBC/diff, lipid panel, renal panel, hepatic panel, troponin I or T, CK, CK-MB, hsCRP, BNP level, and pregnancy test (women of childbearing age))
- Assays for the detection of HIV and HCV (by nucleic acid testing), anti-HIV I/II, anti-HTLV I/II, anti-HBc antibody (Ab), HBsAg, anti-HCV, and Treponema pallidum (by serology) are collected per local site's standard operating procedure.\*
- Echocardiogram (LVEF <45%) (send to echo core lab following study product randomization)\*
- 12 lead ECG

¥ Infectious disease testing can be done on Day 3.

NOTE: The treatment checklist must be completed and submitted prior to the bone marrow aspiration. Subjects who fail the checklist will be excluded from the study.

## 6.3 Day 3 or Day 7 (Study Product Infusion)

- Incremental medical history
- Physical Exam, including vital signs, height and weight
- Assessment of NYHA class (see Appendix 2)
- Bone marrow aspiration for stem cell harvest
- Study product infusion in catheterization laboratory
- Vital signs pre and post bone marrow harvest and cellular product infusion
- Troponin I or T, CK, CK-MB collected one time on the morning following infusion
- Telemetry after procedure (18-24hrs)
- Cardiac MRI (baseline) All patients undergo cardiac cMRI at Day 3 and those patients randomized to therapy on Day 7 will undergo repeat cMRI on Day 7 (send to MRI core lab following study product randomization)
- Five 10 ml venous blood (purple top tubes) for biorepository FACS and migration analysis
- 10 ml venous blood (green top heparin tubes) for biorepository plasma cryostorage
- Review of medications for changes
- Assess for AEs /serious adverse events (SAEs)

## 6.4 Day 4 or Day 8 (Day after infusion)

- Incremental medical history
- Physical Exam, including vital signs, height and weight
- Assessment of NYHA class
- 12 lead ECG
- Review of past 18-24 hours of Telemetry
- Laboratory Testing (CBC/diff, renal and hepatic panel)
- Two 10 ml venous blood (purple top tubes) for biorepository FACS analysis
- 10 ml venous blood (green top heparin tubes) for biorepository plasma cryostorage
- Review of medications for changes

Assess for AEs/SAEs

## 6.5 MONTH 1

- Incremental medical history
- Physical Exam, including vital signs, height and weight
- Assessment of NYHA class
- 12 lead ECG
- 24 hour Holter
- Laboratory Testing (CBC/diff and hepatic panel)
- Two 10 ml venous blood (purple top tubes) for biorepository FACS analysis
- 10 ml venous blood (green top heparin tubes) for biorepository plasma cryostorage
- Review of medication for changes
- Assess for AEs/SAEs

## 6.6 MONTH 3

- Incremental medical history
- Physical Exam, including vital signs, height and weight
- Assessment of NYHA class
- Laboratory Testing (CBC/diff and hepatic panel)
- Two 10 ml venous blood (purple top tubes) for biorepository FACS analysis
- 10 ml venous blood (green top heparin tubes) for biorepository plasma cryostorage
- Review of medication for changes
- Assess for AEs/SAEs

## 6.7 MONTH 6

- Incremental medical history
- Physical Exam, including vital signs, height and weight
- Assessment of NYHA class
- Laboratory Testing (CBC/diff and hepatic panel)
- BNP level
- Echocardiogram (Limited) (send to echo core lab)\*
- Two 10 ml venous blood (purple top tubes) for biorepository FACS analysis
- 10 ml venous blood (green top heparin tubes) for biorepository plasma cryostorage
- 12 lead ECG
- Cardiac MRI (send to MRI core lab)
- Review of medication for changes
- Assess for AEs/SAEs

## 6.8 MONTH 12

- Incremental medical history
- Physical Exam, including vital signs, height and weight
- Assessment of NYHA class
- Laboratory Testing (CBC/diff and hepatic panel)
- BNP level
- Cardiac MRI
- Review of medication for changes
- Assess for AEs/SAEs
### 6.9 MONTH 24

- Incremental medical history
- Physical Exam, including vital signs, height and weight
- Assessment of NYHA class
- Laboratory Testing (CBC/diff and hepatic panel)
- BNP level
- Cardiac MRI
- Review of medication for changes
- Assess for AEs/SAEs

#### \*Echo Contrast Information for Baseline and Month 6

The site will use its clinical judgment to determine if echo contrast (as an aid in visualization of the ventricular endocardial border definition) will be obtained, following these guidelines

- A All echos must include a non contrast component, including collection of data measures before the addition of contrast.
- B If not contraindicated, a contrast component will be obtained

C - If contrast is included in the baseline echo then the 6 month echo visit must also add echo contrast.

#### 6.10 Biospecimens

# Creation of a CCTRN Biorepository for patient blood, bone marrow, and progenitor cell samples.

Recently, a loss in the number of circulating endothelial progenitor cells (EPCs) and a defect in their ability to migrate were shown in patients at increased risk of coronary artery disease, including acute MI. However, these observations are in contrast to a recent study that showed an increased number of EPCs in circulation following AMI. This disparity reflects how little is known about circulating progenitor cells and their impact on cardiovascular disease.

The goal of this biorepository is three-fold: 1) to provide **storage of critical biomaterials** derived from patients enrolled in clinical protocols within the Cardiovascular Cell Therapy Research Network 2) to provide **long-term integrity** (up to 10 years) of these specimens and samples, and 3) to provide progenitor cell profiles and cytokine analyses of samples obtained during the clinical protocols undertaken by the CCTRN with an aim toward gaining insight into diagnostics of disease progression and prognostics of successful intervention. A central CCTRN biorepository will be established at the Center for Cardiovascular Repair at the University of Minnesota and maintained by [name] and her associates. Specifically, [name] group will store these cells in cryovials, up to 10 years, in the University of Minnesota Masonic Cancer Center Liquid Nitrogen Storage Facility. In addition, the CCTRN biorepository will carry out a collection of prospectively described analyses as discussed in Section 5.4.7.

These stem cells will be used for research purposes only (not for profit), will be stored without personal identifying information, and will be shared with approved researchers who will conduct studies to improve the understanding of the effects of cell therapies. Cell samples will be destroyed after 10 years.

<The rest of this page left intentionally blank>

Table 11 provides a summary of the schedule.

	Day 1 or 2 (Consent)	Day 3/7 (SPI)	Day4/8	Мо 1	Mo 3	Mo 6	Mo 12	Мо 24
Complete Medical History	Х							
Incremental Medical History		Х	Х	Х	Х	Х	Х	Х
Informed Consent	Х							
Physical Exam	Х	Х	Х	Х	Х	Х	Х	Х
Laboratory Tests	Х	Х	Х	Х	Х	Х	Х	Х
Pregnancy Test*	Х							
Echo	Х					Х		
ECG	Х		Х	Х		Х		
Bone Marrow Aspiration		Х						
Biorepository Blood Draws		Х	Х	Х	Х	Х		
Cardiac MRI		Х				Х	Х	Х
Study Product Infusion (SPI)		Х						
Medication Review	Х	Х	Х	Х	Х	Х	Х	Х
AE/SAE Evals		Х	Х	Х	Х	Х	Х	Х
Telemetry (18-24 hrs post SPI)		Х						
Holter				Х				

**Table 11.** Schedule of Procedures in TIME (Day 0 is the day of revascularization)

\* In women of childbearing age

**ECHO will be performed at 12, and 24 months if MRI becomes contraindicated** The cardiac MRI's obtained at 12 and 24 months are collected to identify safety findings such as changes in myocardial perfusion, wall motion abnormalities, and the presence of left ventricular thrombus

### 7.0 EVENT REPORTING

### 7.1 Types of Events

### 7.1.1 Adverse Events (AEs)

An adverse event is any untoward medical occurrence in a clinical investigation subject which has been consented, administered a product or medical device. The event need not necessarily have a causal relationship with the treatment or usage.

Examples of adverse events include but are not limited to: abnormal test findings, clinically significant symptoms and signs, changes in physical examination findings, and hypersensitivity. Additionally, they may include the signs or symptoms resulting from drug misuse and drug interactions.

### 7.1.2 Serious Adverse Events (SAEs)

A serious adverse event or serious adverse drug reaction is any untoward medical occurrence at any dose that (1) Results in death; (2) is life-threatening (immediate risk of death); (3) requires inpatient hospitalization or prolongation of existing hospitalization; (4) results in persistent or significant disability/incapacity; or (5) results in congenital anomaly/birth defect.

Examples of serious adverse events include but are not limited to: acute coronary syndrome, pulmonary embolus, and serious ventricular arrhythmias.

### 7.2 Role of Abnormal Test Findings and Hospitalizations in Classifying an Event

### 7.2.1 Abnormal Test Findings

If a test result is associated with accompanying symptoms, and/or the test result requires additional diagnostic testing or medical/surgical intervention, and/or the test result is considered to be an adverse event by the investigator or DCC it should be reported as an adverse event.

NOTE: Merely repeating an abnormal test, in the absence of any of the above conditions, does not constitute an adverse event. Any abnormal test result that is determined to be an error does not require reporting as an adverse event.

### 7.2.2 Hospitalizations

Adverse events reported from studies associated with hospitalization or prolongations of hospitalization are considered serious. Admission also includes transfer within the hospital to an acute/intensive care unit (e.g., from the cardiac wing to the medical floor for an infection, or from the medical division to the neurologic unit for a stroke).

Hospitalization does not include rehabilitation facilities, hospice facilities, respite care (i.e., caregiver relief), skilled nursing facilities or homes, routine emergency room admissions, same day surgeries (as outpatient/same day/ambulatory procedures)

Hospitalization or prolongation of hospitalization in the absence of a precipitating, clinical adverse event is not in itself a serious adverse event.

### 7.3 Reporting Responsibilities of the Investigator

For all events (adverse events and serious adverse events), monitoring and reporting to the DCC begins at the time that the subject provides informed consent, which is obtained prior to the subject's participation in the study, i.e., prior to undergoing any study related procedure and/or receiving investigational product, through and including 30 calendar days after the subject completes the study. Adverse events (serious and non-serious) should be recorded on the eCRFs (AE form and SAE form). **Do not delay the** 

### initial reporting of a serious adverse event in order to obtain resolution or followup information.

For all adverse events, the investigator must pursue and obtain adequate information both to determine the severity and causality of the event. For adverse events with a causal relationship to the investigational product, follow-up by the investigator is required until the event or its sequelae resolve or stabilize at a level acceptable to the investigator, and the DCC concurs with that assessment.

In the rare event that the investigator does not become aware of the occurrence of a serious adverse event immediately (i.e., if an outpatient study subject initially seeks treatment elsewhere), the investigator is to report the event within 24 hours after learning of it and document the time of his/her first awareness of the adverse event.

### 7.3.1 Severity Assessment

The investigator will use the adjectives MILD, MODERATE, or SEVERE to describe the maximum intensity of the adverse event. For purposes of consistency, these intensity grades are defined as follows:

MILD	Does not interfere with subject's usual function.
MODERATE	Interferes to some extent with subject's usual function.
SEVERE	Interferes significantly with subject's usual function.

Note: A severe event is not necessarily a serious event. For example, a headache may be severe (interferes significantly with subject's usual function) but would not be classified as serious unless it met one of the criteria for serious adverse events, listed above.

### 7.3.2 Causality Assessment

If the investigator does not know whether or not investigational product caused the event, then the event will be handled as "possibly related to investigational product" for reporting purposes.

The investigator will use the adjectives below in the determination of whether there ex- ists a reasonable possibility that the investigational product caused or contributed to an adverse event.				
PROBABLE	AEs that are considered, with a high degree of certainty, to be related to the study product.			
POSSIBLE	AEs in which the connection with the study product adminis- tration appears unlikely but cannot be ruled out with certainty.			
UNLIKELY	AEs that are likely produced by the patient's clinical state, environment, toxic factors or other modes of therapy adminis- tered to the patient.			
UNRELATED	AEs that are judged to be clearly and incontrovertibly due on- ly to extraneous causes (disease, environment, etc.)			

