#### 7.3.3 Expectedness Assessment

EXPECTED	Any AE or SAE for which the nature or severity is consistent with information in the Investigator Brochure
UNEXPECTED	Any AE or SAE for which the nature or severity is not consis- tent with information in the Investigator Brochure

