### 7.4 Reporting Responsibilities of the Sponsor (DCC)

### 7.4.1 Sponsor Reporting Requirements to the Executive Committee, NHLBI and DSMB

The DCC-PI will notify the Executive Committee, NHLBI and DSMB of the occurrence of any death or unexpected and associated SAE (i.e. associated with the study product or study procedures) within 72 hours of the DCC receiving notification of the event. This will be followed by a written report no later than seven days after the DCC's initial notification of the event's occurrence. For all other SAEs, the DCC-PI will notify the Executive Committee, NHLBI, and DSMB no later than 15 days of the DCC receiving notification of the event. This will be followed by a written report no later than 30 days after the DCC's initial notification of the event. This will be followed by a written report no later than 30 days after the DCC's initial notification of the event's occurrence. The timing and contents of these reports are governed by the CCTRN *Guidelines for Reporting to Data Safety and Monitoring Board (DSMB)*.

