### 7.4.2 Sponsor Reporting Requirements to FDA

Once the DCC has been notified of a SAE the following are the DCC's reporting requirements to the FDA:

- Fatal or life-threatening, unexpected SAE's and associated with the study drug must be reported to the FDA within 7 calendar days
- Other SAE's that are non-fatal or life-threatening, but are unexpected and associated with the study drug use must reported to the FDA with 15 calendar days

These 7-day and 15-day reports can be satisfied by completion of the FDA From 3500A (MedWatch Form), as well as any source documents as they relate to the event.

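### Two ratings that gate expedited safety reporting are mis-specified: EXPECTED and UNEXPECTED overlap, and causality is rated for the product but not for study procedures

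*Protocol*

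**What the plan says.** **Reporting routes.** Protocol section 7.4.1 has the DCC notify the Executive Committee, NHLBI and DSMB within 72 hours of any death, and of any SAE that is unexpected and "associated with the study product or study procedures", with a written report by day 7. Every other SAE is notified within 15 days, with a written report by day 30. Section 7.4.2 sets the FDA route: "Fatal or life-threatening, unexpected SAE's and associated with the study drug must be reported to the FDA within 7 calendar days". Non-fatal SAEs that are unexpected and associated with the study drug go to the FDA within 15 days.

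**Causality (7.3.2).** The investigator judges whether there is "a reasonable possibility that the investigational product caused or contributed to an adverse event". PROBABLE is "AEs that are considered, with a high degree of certainty, to be related to the study product". POSSIBLE applies when a link with administration of the product seems unlikely but cannot be excluded. UNLIKELY is "AEs that are likely produced by the patient's clinical state, environment, toxic factors or other modes of therapy". UNRELATED is kept for clearly extraneous causes. A default applies "If the investigator does not know whether or not investigational product caused the event": the event is then handled as possibly related to the product.

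**Expectedness (7.3.3).** EXPECTED is "Any AE or SAE for which the nature or severity is consistent with information in the Investigator Brochure". UNEXPECTED uses the same either-or wording, with the consistency negated.

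**The concern.** The fast routes depend on two labels: unexpected and associated. If a label is ambiguous, or is never collected for part of what the trigger covers, two sites can file the same event on different routes and both comply with the protocol.

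This matters because the intervention is invasive in both arms. Placebo patients also have marrow aspiration (3.2.4), and active or placebo infusate is given by catheterization with repeated occlusive balloon inflation (5.3). Section 11.4.3.1 itself describes harms from aspiration, vascular access and interrupted anticoagulation. Section 7.4.1 evidently means procedural SAEs to reach the DSMB quickly when they are unexpected. What is at stake is the speed of safety oversight, not any efficacy estimate.

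**Working it through.** The plan gives no figure to reproduce here, so the check sets the definitions against the triggers.

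**Step 1. Expectedness.** Let N mean that nature is consistent with the Brochure, and S that severity is. As written, EXPECTED = N or S, and UNEXPECTED = (not N) or (not S).

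| Nature | Severity | EXPECTED? | UNEXPECTED? |
|---|---|---|---|
| consistent | consistent | yes | no |
| consistent | not consistent | yes | yes |
| not consistent | consistent | yes | yes |
| not consistent | not consistent | no | yes |

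Two of the four combinations meet both definitions. One is a known type of event at greater severity; the other is a new type at a known severity. This counts logical cases. It does not estimate how often they occur.

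**Step 2. What the label changes.** Suppose an event in row 2 or 3 is filed as EXPECTED.
- A non-fatal SAE associated with product or procedures goes to the DSMB within 15 days instead of 72 hours. Since 72 / 24 = 3 days, the ratio of limits is 15 / 3 = 5. The written report moves from day 7 to day 30.
- A product-associated fatal or life-threatening SAE no longer meets the FDA 7-day condition. A product-associated non-fatal SAE likewise drops out of the FDA 15-day condition.
- A death still reaches the DSMB within 72 hours, because 7.4.1 puts no expectedness condition on deaths.

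**Step 3. Causality against the trigger.**

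| Place | What it covers |
|---|---|
| 7.3.2 question, PROBABLE and unknown-cause default | product |
| 7.3.2 POSSIBLE | administration of the product |
| 7.4.1 trigger | product or procedures |
| 7.4.2 trigger | study drug |
| 7.3 follow-up to resolution | product |

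The only mismatch is between 7.3.2 and 7.4.1. Sections 7.3 and 7.4.2 are product-based, as 7.3.2 is.

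**Step 4. Trace one case.** Take a non-fatal SAE, unexpected against the Brochure, caused by marrow aspiration, vascular access or interruption of anticoagulation. The investigator may properly rate it UNLIKELY or UNRELATED to the product. No rating in 7.3 then marks it as procedure-associated, and 7.4.1 does not say which grades count as associated. It can take the 15-day route although 7.4.1 intends 72 hours.

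**Step 5. Test the remedy.** With EXPECTED = N and S, and UNEXPECTED unchanged, row 1 is EXPECTED only and rows 2 to 4 are UNEXPECTED only. The definitions become exclusive and cover every case.

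**The case against.** The strongest reply is that little would be missed in practice. Several parts of it stand.

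- A row 2 or 3 event also meets UNEXPECTED literally, so a careful reader would apply the fast route. True, but EXPECTED is equally compliant, and the protocol has no tie-break.
- Balloon inflation is how the product is given, so POSSIBLE may cover infusion-time events, and the unknown-cause default adds cover because the infusing investigator is blinded. This stands. The gap is clearest for aspiration, vascular access and interrupted anticoagulation.
- The DCC makes the notification and may judge procedural association itself. This stands, but no defined rating supports that judgment.
- Section 7.5 covers procedures and unexpected severity, and 7.6 names events such as marrow-site bleeding. Both help in part. Section 7.5 also requires a suggestion of greater risk than previously known and uses a grade, definitely, that 7.3.2 lacks. Section 7.6 applies the SAE reporting criteria without adding a causality rating.

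A reader might go further and infer that the procedural harms listed in 11.4.3.1 will generally miss the fast routes. The documents do not support that. The Brochure is not shown, and any harm it lists at that severity is expected and takes the 15-day route whatever its causality grade. Nor does anything show that procedural events are the likeliest to be rated UNLIKELY or UNRELATED. It would also be too strong to say that no site record could trigger the procedural half of 7.4.1: the eCRFs and the separate DSMB reporting guidelines are not shown, and 7.3 asks for adequate information on causality in general.

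**Conclusion.** Both defects are in the current text. The expectedness overlap is a plain logical error in 7.3.3 and needs no assumption about procedures. The causality gap is a mismatch between what 7.4.1 triggers on and what 7.3.2 collects.

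The consequence is that some SAEs can be notified later than intended: up to 15 days instead of 72 hours to the DSMB for a non-fatal SAE, and loss of the FDA 7-day report for a product-associated fatal or life-threatening SAE labelled EXPECTED. The first assumes that the ambiguous label is resolved toward EXPECTED, or that a truly unexpected, procedure-only SAE is not recognised as such by the DCC. The second assumes only the EXPECTED label. How often either would happen cannot be estimated from the protocol.

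A reader might also treat the product-only wording of follow-up in 7.3 and FDA reporting in 7.4.2 as errors. They are not: both agree with 7.3.2, and nothing in the protocol says that procedural events belong there. Because every SAE still reaches the DSMB within 15 days, this should be fixed but does not block the trial.

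**What to change.** 1. In 7.3.3, define EXPECTED as nature and severity both consistent with the Brochure. Leave UNEXPECTED unchanged.
2. In 7.3.2, add a separate relatedness rating for study procedures (marrow aspiration, catheterization and balloon occlusion, interruption of anticoagulation, study imaging), on the same four grades.
3. In 7.4.1, state that associated means PROBABLE or POSSIBLE on either rating.

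Extending follow-up to resolution (7.3) and FDA reporting (7.4.2) to procedure-related events is optional alignment, for the sponsor to decide.

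The cost is protocol wording, one extra field on the AE/SAE eCRF and a few more expedited reports.
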